The specific aims of this pilot study are: **Aim 1)** *To identify whether no prep ready to eat meals (intervention) or ingredient bundles (control) have higher client acceptability, liking, satisfaction, and perceived diet quality ratings.* **Hypothesis:** No prep ready to eat meals will have higher client acceptability, liking, satisfaction, and perceived diet quality scores than ingredient bundles. **Rationale:** Previous research has shown that acceptance, liking, satisfaction, and perceived diet quality are important determinants of the foods people are willing to eat and the ultimate success of diet-related interventions¹². Aim 1 will establish which strategy is most acceptable and desirable for food pantry clients to inform the development of a future randomized-controlled trial that will aim to test which strategy is most effective at improving objective dietary quality and reducing health-related risk factors. **Aim 2)** *To identify whether no prep ready to eat meals (intervention) or ingredient bundles (control) have higher feasibility ratings with food pantry staff.* **Hypothesis:** No prep ready to eat meals will have higher feasibility ratings than ingredient bundles among pantry staff. **Rationale:** It's unclear how much staff time and pantry resources are needed to put together an ingredient bundle from a recipe or store no prep ready to eat meals in appropriate refrigeration units. This pilot study will determine the resources needed to carry out each program and determine which is preferable and feasible for the pantry staff that would be asked to carry out either model given that staff buy-in is a key component to intervention success¹³.

2. Background.

- Describe past experimental and/or clinical findings leading to the formulation of your study.
- For research involving investigational drugs, describe the previously conducted animal and human studies.
- For research that involves FDA approved drugs or devices, describe the FDA approved uses of this drug/device in relation to your protocol.
- Attach a copy of the approved labeling as a product package insert or from the Physician's Desk Reference.

You may reference sponsor's full protocol or grant application (section number and/or title) or if none, ensure background includes references.

Please respond to all components of this item, or clearly indicate which components are not applicable.

a. Background

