To test the second hypothesis, I will use a mixed-methods approach with food pantry staff (N=10), including questionnaires with fixed and open-ended items on feasibility and satisfaction of each distribution strategy followed by 30-minute semi-structured 1-1 interviews conducted by UT Southwestern study staff.

4. Research Plan / Description of the Research Methods:

4.a. Provide a comprehensive narrative describing the research methods.

- 1) Provide the **order in which tests/procedures will be performed**,
- 2) Provide the **setting** for these events and a description of the **methods used to protect privacy** during the study.
- 3) Provide the **plan for data analysis** (include as applicable the **sample size calculation**)

Please respond to all components of this item, or clearly indicate which components are not applicable.

C.1.5 Intervention Methods

After completing consent forms, participants will be randomized to receive no prep ready-to-eat meals or ingredient bundles using random number generation. Participants will be unaware of their assignment until they are asked to select study meals, in which case it will be obvious because of the food items available to select. Participants will complete questionnaires and then select meals – they can select up to 2-meals, or the bundles needed to make 2-meals, for 14-days for themselves and 2 additional members of their household. Participants will elect to receive one week of meals after selection and come back to pick-up the second week of meals or they will take home all study meals at one time (participants choice). Participants will return at the end of the 2-week study period to complete the follow-up questionnaires and receive payment. A study timeline of intervention components and data collection is provided in **Table 1** to aid visualization of the study plan and timeline for **food pantry clients**.

Table 1. Study plan and timeline for food pantry clients.

Baseline appointment (Day 0)	Intervention (Day 1 - Day 14)	Follow-up appointment (Day 15)

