
 1. Informed consent 2. Randomization 3. Questionnaires (demographics, current pantry use, acceptability, satisfaction, liking, diet quality) 4. Selection of preferred no prep ready-to-eat meals OR ingredient bundles from the available study foods depending on study assignment 5. Follow-up appointment scheduled 	
 1. Participants and family members consume no prep ready-to-eat meals or ingredient bundles at-home for 14-days 2. Depending on the client's preference, reminder phone calls, texts, and/or emails are sent leading up to their follow-up appointment 	
 1. Questionnaires (demographics, current pantry use, acceptability, satisfaction, liking, diet quality) 2. Participant thank you and payment

C.1.5.1 No prep ready-to-eat meals

Roots Food Group provides nutrient-dense dietitian developed no prep ready-to-eat meals to many of the 14 million people on Medi-Cal in California through Aetna and HealthNet. The community-based 501c3 arm of Roots Food Group, Roots Food Foundation, provides the same meals and other resources to people living with blindness at no cost. Roots Food Foundation has agreed to donate and supply meals for this study.

Pantry clients will select study meals for up to 14-days' worth of meals for themselves and 2-members of their household using Crossroads online food selection platform (this platform is already built and is how clients currently select pantry foods). Roots Food Group produces over 70 meals. We have elected to study 14-days of meals to offer clients variety and determine which flavors are most desirable to clients. After ordering, meals will be retrieved from a refrigeration unit, boxed by pantry staff, and brought to the participant to take home. An example dinner is "Teriyaki Chicken with Roasted Potatoes and Broccoli", and an example breakfast is "Omelet with Peppers and Zucchini". Meals can be stored in a refrigerator or freezer and eaten immediately or after reheating depending on the meal and consumer preference. 94% and 86% of Crossroads clients reported owning a refrigerator and microwave respectively when previously surveyed²⁷ and microwaves are available in many community centers and gas stations for public use. This makes no prep ready-to-eat meals a potential solution to many of the challenges faced by Crossroads pantry clients and people experiencing food insecurity.

C.1.5.2 Ingredient bundles

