At the baseline appointment participants will complete informed consent and a questionnaire that includes demographics, typical food pantry utilization, satisfaction, acceptability, liking, and perceived diet quality. Satisfaction items will be adapted from previously validated food pantry client satisfaction surveys (e.g., "How satisfied are you with the amount/variety/frequency of food that you and others in your household receive at this food pantry?")²⁸. Possible responses range from very satisfied and somewhat satisfied to somewhat dissatisfied and very dissatisfied. Liking of study foods will be measured by showing the name and picture of the meal or ingredient bundle and asking participants to respond to a hedonic 9-point bipolar scale with four measures of liking and four measures of dislike and a neutral "neither like nor dislike" item²⁹. Acceptability will be measured by showing the name and picture of the meal and asking the client whether they and/or members of their household ate the meal within the past 2-weeks and whether they would select the meal again if given the opportunity in the future³⁰. Perceived dietary quality will be measured using a single validated item that asks participants to rate their overall diet quality as "excellent," "very good," "good," "fair," or "poor"³¹. At the follow-up appointment, participants will complete the same liking and acceptability ratings, and a similar satisfaction questionnaire and perceived diet quality item, except wording will be slightly modified to "How satisfied were you with the amount of food that you and others in your household received at the food pantry **in the past 2-weeks?**" "How would you rate your dietary quality **over the past 2-weeks?**". These measures will allow us to determine between-group

Form A

IRB # STU 2022-0809

differences at baseline as well as within- and between-group changes in acceptability, satisfaction, liking, and diet-quality after consuming meals over time. These measures will also identify client's preferred meal flavors and frequency as well as the quantity desired in a future intervention.

C.1.6.2. Pantry Staff Measures

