 N/A - this study does not test or evaluate an intervention. Skip to item 4.d.			
#	Study intervention(s) being tested or evaluated under the protocol Add or delete rows as needed	Affiliate	Local Standard Practice? Indicate whether the intervention is considered acceptable practice locally for applicable institutions
1	
Figure 1. Example no prep ready-to-eat meals
  
Image Citation: https://www.supermarketnews.com/deli/spartannash-debuts-private-label-ready-made-meals
	 UTSW  PHHS  CMC  THR  TSRH  Other: Crossroads Community Services (Food pantry)	 Yes  Yes  Yes  Yes  Yes  Yes
2	
Figure 2. Example ingredient bundles or "meal kits"
  
Image Citation: https://www.everydayhealth.com/high-cholesterol/the-best-meal-kits-for-people-with-high-cholesterol/
	 UTSW  PHHS  CMC  THR  TSRH  Other: Crossroads Community Services (Food pantry)	 Yes  Yes  Yes  Yes  Yes  Yes

4.c. Risk:Benefit Analysis of study interventions being tested or evaluated under this protocol

For each study intervention identified in section 6b above, complete a risk:benefit analysis table.

(Two tables are provided, copy & paste additional tables as needed or delete both tables if this study does not test an intervention)

Form A

IRB #	STU 2022-0809
-------	---------------

4.c.

Study Intervention #1

No prep ready to eat meals

List each group exposed to this intervention on a separate line. (e.g., experimental, control, Arm A, Arm B, etc) Or state All Groups/Subjects	For each group, list the benefits of this intervention. (Benefits can be directly from the intervention or from a monitoring procedure likely to contribute to the subject's wellbeing). If there are no benefits, state "none".
Experimental	Participants, many of whom are food insecure, receive extra free food as a part of this study

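### The satisfaction wording shown rates food from the pantry as a whole, not the assigned meals or bundles, so the Aim 1 satisfaction comparison may be diluted by an unknown amount

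*Combined protocol and SAP*

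**What the plan says.** The Aim 1 hypothesis sets the two food strategies against each other: "No prep ready to eat meals will have higher client acceptability, liking, satisfaction, and perceived diet quality scores than ingredient bundles".

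C.1.6.1 (Pantry Client Measures) gives an example of the baseline satisfaction items: "How satisfied are you with the amount/variety/frequency of food that you and others in your household receive at this food pantry". At follow-up a similar questionnaire is used, with the time frame moved to the past two weeks. The example shown is "How satisfied were you with the amount of food that you and others in your household received at the food pantry". In both examples the thing being rated is food from the pantry.

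The same section ties the other study-food ratings to the study food itself. For liking: "Liking of study foods will be measured by showing the name and picture of the meal or ingredient bundle". Acceptability is likewise asked with the name and picture of the meal.

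Section 4.c gives the same benefit for both arms: "Participants, many of whom are food insecure, receive extra free food as a part of this study". Table 1 lists these questionnaire topics at both Day 0 and Day 15: "demographics, current pantry use, acceptability, satisfaction, liking, diet quality". C.1.7.1 forms a sum score for satisfaction and analyses it by repeated-measures ANOVA for group and group-by-time effects. It plans no separation of usual pantry food and no adjustment for it.

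**The concern.** The hypothesis is about satisfaction with a strategy, while the wording shown measures satisfaction with everything received at the pantry. If households go on collecting ordinary pantry food during the two weeks, part of each answer concerns food that is not randomised, and that part pulls the arms together. The one follow-up item shown is also about amount, and the limit on study food is the same in both arms.

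Aim 1 is meant to show which strategy is more acceptable and desirable, to inform a later randomised trial. With this wording, similar satisfaction scores could mean that clients were equally satisfied with meals and bundles, or that a difference was masked by the rest of their pantry food. The score alone could not tell these apart.

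**Working it through.** **Figures in the plan.** Section 3 gives 35 participants per arm. The plan states no significance level, power, effect size, SD or dropout for satisfaction, so it has no figure to reproduce.

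**What each item rates.**
- Liking: the named and pictured meal or bundle.
- Acceptability: the named and pictured meal.
- Satisfaction, at baseline and follow-up as illustrated: food the household received at the pantry.
- Perceived diet quality: the whole diet, by design.

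So among the four Aim 1 outcomes, only satisfaction is aimed at the study food in the hypothesis but at a wider object in the wording shown.

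**Amount of study food.** C.1.5 says of both arms: "they can select up to 2-meals, or the bundles needed to make 2-meals, for 14-days for themselves and 2 additional members of their household". The ceiling is 2 meals × 14 days × 3 people = 84 person-meals in each arm. It is a limit, not a fixed ration, so uptake may differ.

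**Illustration of dilution.** Inputs assumed here, not taken from the plan: two-sided 5% test, two-sample t-test at follow-up, no dropout, true difference in satisfaction with study food d = 0.68 SD. The value 0.68 is chosen because it gives 80% power with 35 per arm when undiluted (the exact t-test solution is 0.679).

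Let the rating be w × (satisfaction with study food) + (1 − w) × (satisfaction with other pantry food). Both parts have SD 1 and correlation r, and the other part does not differ by arm. Then:

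- SD of the rating = √[w² + (1 − w)² + 2w(1 − w)r]
- visible effect = w × 0.68 ÷ SD of the rating
- power from the noncentral t distribution, 68 degrees of freedom, noncentrality = visible effect × √(35/2)

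| Share w | Correlation r | SD of rating | Visible effect | Power |
|---|---|---|---|---|
| 1 | – | 1 | 0.68 | 80% |
| 0.75 | 0 | 0.791 | 0.645 | 76% |
| 0.75 | 0.5 | 0.901 | 0.566 | 65% |
| 0.75 | 1 | 1 | 0.51 | 56% |
| 0.5 | 0 | 0.707 | 0.481 | 51% |
| 0.5 | 0.5 | 0.866 | 0.393 | 37% |
| 0.5 | 1 | 1 | 0.34 | 29% |

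Example, w = 0.5 and r = 0: SD = √(0.25 + 0.25) = 0.707, and 0.5 × 0.68 ÷ 0.707 = 0.481.

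The lowest figure at each share needs satisfaction with the two food sources to be perfectly correlated. Within r from 0 to 1 it is the worst case, so it should not be quoted alone.

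**The case against.** The strongest reply is that the questionnaire is not in the documents. C.1.6.1 introduces the satisfaction items as an example and calls the follow-up version similar, so an item on study food may exist that the reader cannot see. This stands, and it is why the point is put as a possible dilution. A reader might infer that the satisfaction outcome is shown to be diluted, or fails to measure the strategies at all. The documents do not support either reading.

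Study food is collected at the pantry within the window the item names, and may reach 84 person-meals. The documents do not say how much ordinary pantry food a household receives in those two weeks, and the phrase "receive extra free food as a part of this study" comes from a benefit line in the risk:benefit form, not from a description of concurrent collections. The study-food share could be close to 1. This stands too: the size is unknown.

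A reader might also infer that the score has little reason to differ between arms because the item shown is about amount. That goes too far. Amount is one of three facets in the baseline example, variety can plausibly differ, and the amount is only capped equally.

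The power figures come from an assumed model and a follow-up t-test, whereas the plan uses repeated-measures ANOVA. The baseline item may remove some stable variation due to ordinary pantry food. The figures therefore illustrate a range and do not forecast this trial's power.

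Finally, the pantry-wide wording has a purpose. No participant has received study food at baseline, so only a general item can be asked at both visits, and C.1.6.1 wants change over time. This is a good reason to keep the item. It does not make the item a direct answer to the Aim 1 question.

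**Conclusion.** The point holds in a limited form. As illustrated, the satisfaction items rate pantry food in general, study food is described as additional, and nothing says that usual pantry food stops. The score may therefore partly rate food that does not differ by arm, and a null result would be hard to read as equal satisfaction with the two strategies.

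The size cannot be determined from the documents. Under the assumptions above, power for a difference that would have 80% undiluted lies between 56% and 76% at a three-quarter share, and between 29% and 51% at a half share. If the share is close to 1, the loss is negligible.

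Severity is minor to moderate. Satisfaction is one of four Aim 1 outcomes in a pilot, and liking and acceptability already name the study foods. A reader might infer that a real preference for one strategy would go undetected by the trial. The documents do not support that, because acceptability asks directly whether the client would choose the meal again.

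**What to change.** At Day 15, add the amount, variety and frequency items again, worded for the ready-to-eat meals or ingredient bundles that the participant received in this study. Use the same facets and response options in both arms, and add no item that favours one arm by construction, such as ease of preparation.

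In C.1.7.1, add a sentence stating that the score of these items is compared between arms at follow-up as the direct Aim 1 comparison of satisfaction with the strategies. Keep the pantry-wide items and the planned repeated-measures ANOVA unchanged, and report them as change in satisfaction with the pantry. If the questionnaire already contains study-food items, it is enough to say so and to name them in C.1.7.1.

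The cost is two or three extra questions and one sentence. The new items have no baseline, so they support a between-arm comparison at follow-up only. Randomisation makes that comparison valid.

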have cutting knives or a blender²⁶, these are kitchen tools frequently recommended for healthier meal preparation strategies and required to prepare many recipes, such as stir fries, smoothies, and casseroles.

No prep ready-to-eat meals alleviate the time and food preparation constraints faced by people experiencing food insecurity and provide the opportunity to encourage more nutritious food consumption in a potentially preferable package. While market research and consumer scientists have identified no prep ready-to-eat meals as a burgeoning food retail avenue²⁶, these meals have not been empirically tested as a strategy for improving food security, dietary quality, and health outcomes among clients in a food pantry setting. Given the novelty of this idea, formative research is needed to confirm the intervention is desirable to food pantry clients and feasible for food pantry personnel to carry out.

b. Current practice

[figure not shown]
Currently, food pantry clients at Crossroads receive food in one of three ways:

- 1) Emergency box filled with food provisions filled by pantry staff – the number of pounds received is dependent on the household size and age of household members, the pantry client does not get to choose the food they receive
- 2) With an appointment, clients walkthrough the pantry and select food off shelves and from inside refrigeration units based on a point system – points are distributed based on household size and age of household members and the pantry inventory, the pantry client chooses the food they receive
- 3) With an appointment, clients select food using a web-based application that displays live inventory. Clients select food using the application based on the same in-house point system, the pantry client chooses the food they receive

3. Study Design.

Describe the study design (e.g., single/double blind, parallel, crossover, etc.) Consider inserting a scheme to visually present the study design.

Figure 3. Proposed study design

To test the first hypothesis, I will use a randomized repeated measures between-subjects design with half of the participants randomized to receive 14-days of no prep ready-to-eat meals (intervention, n=35) and half of the participants randomized to receive 14-days of ingredient bundles (control, n=35) (Figure 3).

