Food pantry staff will answer feasibility items for each of the intervention groups, such as desire to implement each food distribution strategy in the future, perceived appropriateness of the intervention given their organizational goals, perceived sustainability, and financial/staff resources needed to carry out the intervention longer term³². Staff participants will also respond to qualitative open-ended response items such as "Describe any challenges experienced with distributing ingredient bundles" "Describe any challenges experienced with distributing no prep ready-to-eat meals". Responses to the questionnaire will be followed with 30-minute semi-structured 1-1 interviews with study personnel, which give pantry staff the opportunity to directly voice any challenges or preferences that come up when implementing either approach. The pantry personnel perspective will allow us to design a feasible and sustainable longer-term intervention.

C.1.7. Analytic Plan

C.1.7.1. Analytic Plan for Pantry Client Data

Descriptive statistics (e.g., means, percentages, chi-squared tests of independence) will be used to describe participant characteristics and baseline differences. The independent variable of interest will be randomized group assignment (e.g., no prep ready to-eat-meals vs. ingredient bundles). Spearman's correlation and/or repeated measures Analysis of Variance (ANOVA) will be used to describe the association between group assignment and client's perceived diet quality at follow-up. If normally distributed, repeated-measures ANOVA is acceptable and will be used. If non-normal, Spearman's correlation will be used. For the other three outcomes of interest (satisfaction, acceptability, and liking) sum scores will be calculated, and model assumptions will be tested (e.g. residual distributions) before proceeding with repeated-measures Analysis of Variance (ANOVA) to test for group effects on study outcomes of interest and group-by-time interactions.

C.1.7.2 Analytic Plan for Pantry Staff Data

Descriptive statistics (e.g., means, percentages) will be used to describe quantitative items on staff feasibility and satisfaction. Qualitative thematic analysis of open-ended questionnaires and interviews will be synthesized into key findings and suggestions for future intervention development.

Form A

IRB # **STU 2022-0809**

4.b. List of the study intervention(s) being tested or evaluated under this protocol

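### The acceptability analysis has no covariate, although half of its score counts eating by any household member; one prespecified household-size term would be a cheap, modest gain in precision

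*Combined protocol and SAP*

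**What the plan says.** C.1.7.1 (Analytic Plan for Pantry Client Data) says "The independent variable of interest will be randomized group assignment". For satisfaction, acceptability and liking it forms sum scores and uses repeated-measures ANOVA "to test for group effects on study outcomes of interest and group-by-time interactions". No covariate is named. Section C.1.5 says "participants will be randomized to receive no prep ready-to-eat meals or ingredient bundles using random number generation" and mentions no stratification. Section 3 plans 35 clients per arm.

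C.1.6.1 builds acceptability from two questions about each meal. One is "whether they and/or members of their household ate the meal within the past 2-weeks"; the other is whether the client would choose the meal again. Both are asked at Day 0 and at Day 15, and in Table 1 the Day 0 questionnaires come before any study food is selected.

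Household size appears as a quantity only under Current practice (section 2.b), where "points are distributed based on household size and age of household members and the pantry inventory". The Day 0 questionnaire is described as covering demographics, without naming household size.

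**The concern.** The eating question is answered yes if anyone in the household ate the dish. Unless members always eat the same dishes, a household of three has more chances to score than a person living alone, whichever arm it is in. That variation has nothing to do with the comparison of interest, and it can be removed with a variable that is fixed before allocation.

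Neither the allocation nor the analysis deals with it. At 35 per arm the trial can detect only a fairly large difference, and its results are meant to shape a later randomised trial. Avoidable noise in acceptability is therefore worth removing. The choice also needs to be made now, because a covariate picked after the data are seen invites selective adjustment.

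**Working it through.** **Benchmark.** The plan gives no alpha, power, effect size or SD for its 35 per arm, so there is no figure to reproduce. Assuming two-sided 5% and 80% power, 35 per arm (t test, 68 df) detects 0.679 SD without adjustment.

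**Share of variance explained (R²).** All inputs here are assumptions; the documents give none.
- Households of 1, 2 and 3+ people are equally common, and 14 dishes are scored.
- Each person eats a given dish with probability p = 0.2-0.6.
- Other client-to-client SD in the share of dishes eaten is s = 0.10-0.25.
- The client's own choose-again share has SD b = 0.15-0.25, and correlation c = 0-0.5 with the part of the eaten share not due to household size.
- A fraction w of dish choices is shared by the whole household.

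The chance that a dish is scored as eaten in a household of h people is q(h) = w·p + (1−w)·[1−(1−p)^h]. With p = 0.4 and w = 0, q = 0.40, 0.64 and 0.78 for h = 1, 2, 3.

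Let V = variance of q over h, and r = mean[q(1−q)]/14 + s². For the two-part sum score, R² = V / (V + r + b² + 2c·b·√r).

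- Low end, independent eating (p = 0.2, s = 0.25, b = 0.25, c = 0.5): V = 0.0139, r = 0.0777, so R² = 0.0139/(0.0139 + 0.0777 + 0.0625 + 0.0697) = 6%.
- High end, independent eating (p = 0.45, s = 0.10, b = 0.15, c = 0): V = 0.0252, r = 0.0242, so R² = 0.0252/(0.0252 + 0.0242 + 0.0225) = 35%.

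| Dish choices shared | R², sum score |
|---|---|
| none | 6-35% |
| half | 2-11% |
| three quarters | 0.4-3% |
| all | 0% |

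**One linear term is enough.** With three equally common sizes, the linear part of V is [q(3)−q(1)]²/6. At p = 0.4 and w = 0 this is 0.384²/6 = 0.0246, against V = 0.0251, or 98%.

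**Cost and gain on the Day 15 score.** With one covariate the residual variance is multiplied by (1−R²), the expected inflation from chance imbalance is 1 + 1/66, and 67 df remain (critical t moves from 1.9955 to 1.9960). Rho is the correlation of household size with the score, so R² = rho².

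| rho | R² | Detectable difference | Power at 0.679 SD |
|---|---|---|---|
| 0 | 0% | 0.685 SD | 79.4% |
| 0.2 | 4% | 0.671 SD | 81.0% |
| 0.3 | 9% | 0.653 SD | 83.0% |
| 0.5 | 25% | 0.593 SD | 89.4% |

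Break-even is at rho of about 0.124, that is 0.124² = 1.5% of variance. Below it the loss is at most 80.0 − 79.4 = 0.6 points.

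**Chance imbalance.** The difference between arms in mean household size has SD √(2/35) = 0.239 SD units, and 1.96 × 0.239 = 0.47. An imbalance of 0.47 moves the unadjusted outcome contrast by 0.3 × 0.47 = 0.14 SD at rho 0.3.

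**Group-by-time test.** This was simulated with 8,000 runs per case, an assumed 0.6 SD effect at follow-up and an assumed within-person correlation of 0.5.

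| Household-size effect | Unadjusted power | Adjusted power |
|---|---|---|
| 0.3 at both visits | 73.4% | 72.8% |
| 0.3 at follow-up only | 67.8% | 70.9% |
| 0.5 at follow-up only | 64.0% | 74.3% |

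An effect that is equal at both visits cancels from this test, so the covariate gains nothing there. A gain needs an effect that differs between visits and a model term that allows it. That is plausible for acceptability, because Day 0 precedes any study food.

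**The case against.** The strongest reply is that nothing here is an error. Randomisation makes the unadjusted comparison unbiased on average, this is a pilot, and no document reports a relation between household size and any outcome. All of that stands: the point concerns efficiency, not validity. C.1.7.1 also plans to describe baseline differences, which would make an imbalance visible but would not remove its effect on the estimate.

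A second reply is that shared eating is natural, particularly when a bundle is cooked as one meal. That also stands, and it is why the range runs down to nothing. A reader who modelled the eating question alone, with independent eating, would get 15-51% of variance. That is not the score the plan analyses, since the client's own choose-again answer is added to it.

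A reader might also infer that satisfaction is affected, because study food is supplied "for 14-days for themselves and 2 additional members of their household" while usual pantry points rise with household size. The documents do not establish this. The risk-benefit tables in section 4.c describe the study food as extra, nothing says that usual allocations stop, and amount is only one of several satisfaction items.

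Finally, adjustment is not quite free. Household size is not named as an item on the form, and entering it in four categories would use 3 df instead of 1.

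**Conclusion.** The point holds as a cheap improvement to the acceptability analysis. C.1.7.1 plans no covariate, and the wording of the eating question itself links household size to the score in both arms. The strength of that link is unknown: about 2-35% of sum-score variance with independent to half-shared eating, and near zero if households eat together. These figures rest on the assumed eating probabilities, SDs, household mix and 14 dishes. Against this, the worst case is about 0.6 points of power.

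Two stronger readings should be resisted. The unadjusted arm comparison is not biased by the omission. And the documents do not show that household size drives satisfaction, or by how much.

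**What to change.** In C.1.7.1, prespecify household size capped at three (1, 2, 3+) as a single linear term for acceptability. Use it either in an ANCOVA of the Day 15 score or, if the repeated-measures model is kept, together with a household-size-by-time term; a main effect alone does not help the group-by-time test when the effect is the same at both visits. Report the adjusted arm difference with its 95% CI. Before enrolment, confirm that the Day 0 demographics form records household size. Adjustment of satisfaction can be left optional.

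The cost is a short addition to the analytic plan, one confirmed form item and 1 df in the Day 15 model, with no extra clients.
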